3. SUBJECTS OF STUDY

There is an increase in the prevalence of cervicalgia related to postural habits, new work practices and the use of electronic devices, traffic accidents and population aging. Cervical pain is very frequent with a point prevalence between 10-13%, appearing at some point in life up to 70% of the population. Occurs between 11-14% of sick leave. This situation justifies the feasibility of obtaining the sample required to carry out the study in an adequate time. The sample required for this project according to similar articles will be around 30 subjects per group.

The selection criteria of the sample in this study are as follows.

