5. STUDY VARIABLES

5.1. Independent variables study object

The independent variables of the project are: a) belonging to the control or intervention group; and b) time, according to the timing of pre-intervention and post-intervention measurements. We also recorded as independent variables the general characteristics of the sample: age, BMI, sex, hours of weekly sports activity.

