5.2. Dependent variables

The dependent variables of the study are Romberg index and stabilometric data with open eyes and closed eyes of the variables as follows:

- Mean of the oscillation on the X axis and on the Y axis.
- Length of the oscillation.
- Surface of the ellipse.
- Speed of the oscillation on the X axis and on the Y axis.
- Average speed of the oscillation.

6. STUDY GROUPS.

The sample will be divided into 2 groups: Intervention Group and Control Group. The suboccipital inhibition technic described will be applied to the intervention group. The control group will be given a superficial contact in the same area as the intervention, to rule out the exteroceptive effect associated with the therapist's contact. The subjects will be assigned to both groups through a computerized system of simple randomization.

7. EVALUATION.

The evaluation will be done at the Clinica Osteomed physiotherapy center located in Elche, where tools, space, evaluators and appropriately prepared interveners are available to carry out this project. The evaluation will be carried out in two moments: before the intervention and immediately after it. The time between the pre-intervention measurement and the intervention is less than 15 minutes. The time elapsed between the intervention and the post-intervention measurement will be less than 1 minute. For the evaluation a pressure platform will be used (Diagnostic Support SRL, model "Clinical MultiSensor", 4 sensors / cm², 40 captures / second) and the data will be registered by the Milletrix software (Diagnostic Support V.1.0.0.26). The stabilometric record will be made with aligned heels in a comfortable position for the subject, looking forward at eye level on a wall 5 m from the subject. On both sides there will be two clear panels that will close a 3 m wide corridor. It will remain silent, constant temperature (20°-23°) and good luminosity (2000 Lux). The stabilometric record will have a duration of 52 seconds. The measurement will be made without footwear and the orders given to the subject will be protocolized so that they do not influence their postural attitude unequally.

Stabilometric data with open eyes and closed eyes of the variables, mean of the oscillation on the X axis and on the Y axis, length of the ball, surface of the ellipse, speed of the oscillation on the X axis and on the Y axis, average speed of the oscillation and the Romberg index.

8. STUDY SEQUENCE.

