The study will be carried out in two adjoining rooms with enough space to offer freedom of movement to both the examiner and the subject of study. In one of them will be the evaluator, responsible for making the measurements and collect the pre-intervention and post-intervention values, using a stabilometric platform, a scale with stadiometer and a computer. The time that elapses between the execution of the technique and the start of the post-intervention measurement is, in all cases, less than one minute. In the other room, the intervener will be in charge of performing the randomization after the first measurement and performing the corresponding intervention. It will have a treatment table for the patient and a stool for the intervener. Between both rooms there are approximately eight meters without steps or unevenness.

A. Recruitment: Recruitment will be done after the first physiotherapy consultation. The

physiotherapist will inform the patient of the characteristics of the study and, after checking their eligibility to participate in the study, will proceed to sign the informed consent.

B. Evaluation pre-intervention. The subject of the study begins his participation in the evaluation room. The evaluator performs the pre-intervention evaluation. Following the protocol of the "Association Française de Posturologie" (AFP) the subject will be in a well-lit room (2000 Lux approximately), located on the platform with the heels separated 4 cm and with the tips of the feet forming a 30° angle. You will look forward to a fixed point located 5 meters above your eyes. On both sides, two light colored panels are placed. The width of the tunnel thus formed is 3 meters. In addition the room will be silent and the temperature will be constant between 20° and 23°C so that the physiology of the subject is not altered to the point of feeling cold or sweating. We have decided to use this protocol because they are healthy subjects because, despite being an artificial position, we unify all the subjects in a position of certain instability because their heels are very close and their feet are symmetrical. Each foot is separated 15° of the sagittal plane. We will make the assessment with open eyes and closed eyes to determine the Romberg coefficient.

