9. PROVIDED BENEFITS

The technique proposed in this study should have an impact on the symptoms of instability and balance disorders associated with cervicalgia. The technique under study may be included in the protocols of conservative physiotherapy treatment for patients with cervicalgia and cervicogenic instability.

Statistical Analysis Plan (SAP)

Size Sample and Feasibility

The statistical program that we will use will be SPSS v.20. To determine the sample size, a pilot study will be conducted with the same methodology as the original study to a group of 10 subjects. These subjects will be assigned to the same group. This pilot study will provide us with the estimates of the mean and variance of the response variable, thus being able to calculate the appropriate sample size by determining a minimum power value of 80% ($W > 80\%$) and a confidence level of 95% ($p < 0.05$).

The pilot sample will be part of the final sample to be studied if there are no changes in the protocol or in the variables to be measured.

For the descriptive analysis, the mean and the standard deviation will be calculated. To prove normality, the Kolmogorov-Smirnov test, or Shapiro-Wilk test, and for homoscedasticity the Levene test. To evaluate the pre-post intra-group differences, the t test will be used for related samples (if they are parametric) or the Mann-Whitney U test (if they are nonparametric). For the analysis of pre-post intergroup differences the ANOVA statistic will be used. The significance value is set at $p < 0.05$.

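### The between-group ANOVA on pre-post differences leaves out the pre-randomisation baseline as a covariate; ANCOVA would be at least as precise in nearly all plausible cases, at the cost of one degree of freedom

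*Combined protocol and SAP*

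**What the plan says.** The analysis paragraph of the SAP gives a single sentence to the comparison between groups: "For the analysis of pre-post intergroup differences the ANOVA statistic will be used". It names no outcome form, factors, covariate or effect estimate. Section 5.1 lists group as an independent variable together with "time, according to the timing of pre-intervention and post-intervention measurements". It adds age, BMI, sex and sports hours as recorded characteristics but assigns them to no model. ANCOVA and baseline adjustment are not mentioned anywhere in the document.

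The baseline is available for every variable and cannot have been affected by allocation. Section 8 says that "the intervener will be in charge of performing the randomization after the first measurement", and its steps B and C give the same order. Allocation is by simple randomisation (section 6), with no stratification on baseline. On size, section 3 says: "The sample required for this project according to similar articles will be around 30 subjects per group".

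**The concern.** This comparison answers the trial's question. A change score subtracts the baseline with a fixed slope of 1. With similar spread before and after, the post value regresses on the baseline with a slope of rho, which is below 1. Two consequences follow, and they are two views of one inefficiency. Averaged over randomisations, the estimate varies more than it needs to. In any one randomisation with a chance baseline difference, it is shifted by -(1 - rho) times that difference. At about 30 per group with simple randomisation, nothing in the design limits such differences. What is at stake is power and the credibility of the estimate when the groups happen to differ at baseline. The validity of the test is not in question.

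**Working it through.** **Which test is planned.** The sentence can mean ANOVA on change scores or a group-by-time ANOVA. With one pre and one post measurement these coincide. On a generated data set of 30 per group, the interaction F, the one-way F on change scores and the squared t on change scores were all 2.399.

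**Inputs from the document.** About 30 per group (section 3), significance at 0.05 and power of at least 80% (SAP), and baseline before randomisation (section 8).

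**Assumptions.** Two-sided test, 1:1 allocation, equal pre and post SDs (set to 1), and rho from 0.3 to 0.97. The document gives no rho, SD or effect size.

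**The plan's own figure.** The 30 per group cannot be reproduced, because it is taken from similar articles with no effect or SD stated. Back-solving, 30 per group gives 80% power for a standardised difference of (1.960 + 0.842) x sqrt(2/30) = 0.72 by the normal approximation, or 0.736 with the t distribution. The 0.736 is used below, on the change-score scale. It is an anchor for comparison and not a trial figure.

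**Variances.**
- Change score: 2(1 - rho).
- ANCOVA residual: 1 - rho².
- Ratio ANCOVA/change: (1 + rho)/2. Estimating the slope multiplies the ANCOVA variance by 1 + 1/56 on average.
- Break-even: (1 + rho)/2 x 57/56 = 1 gives rho = 0.965.

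**Chance imbalance.** The SE of the baseline difference is sqrt(2/30) = 0.258 SD. A difference above 0.5 SD in either direction is 0.5/0.258 = 1.94 SEs, which occurs in 5.3% of randomisations. The shift for a one-SE imbalance is (1 - rho) x 0.258.

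**Results.** The assumed effect is 0.736 x sqrt(2(1 - rho)), so that the change score has 80% power in every row. ANCOVA power uses 57 df and is averaged over baseline imbalance.

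| rho | Assumed effect (SD) | Variance ratio | ANCOVA power | One-SE shift of change score (SD) | Shift as % of effect |
|---|---|---|---|---|---|
| 0.3 | 0.87 | 0.66 | 93% | 0.18 | 21% |
| 0.5 | 0.74 | 0.76 | 89% | 0.13 | 18% |
| 0.7 | 0.57 | 0.87 | 85% | 0.08 | 14% |
| 0.8 | 0.47 | 0.92 | 83% | 0.05 | 11% |
| 0.9 | 0.33 | 0.97 | 81% | 0.03 | 8% |
| 0.95 | 0.23 | 0.99 | 80% | 0.01 | 6% |

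At rho 0.97 ANCOVA power is 79.9%. By the normal approximation without the slope charge, ANCOVA would need 20, 23, 26, 27, 29 and 30 per group in these six rows to match the change score at 30.

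**Simulation checks.** With 40,000 trials per rho, ANCOVA power was 93.1%, 89.5%, 85.1%, 83.3%, 81.1% and 80.1%, and type I error was 4.8% to 5.1% for both methods. A separate run of 8,000 trials per scenario (60 subjects, simple randomisation, true difference 0.5 SD) gave mean change-score estimates of 0.501, 0.498 and 0.501 at rho 0.5, 0.7 and 0.9, so the planned test is unbiased on average. In the same run, power for change score and ANCOVA was 47.0% and 57.7%, 67.3% and 73.5%, and 98.7% and 98.8%. Per SD of baseline imbalance the change-score estimate moved by -0.52, -0.31 and -0.10, against about 0 for ANCOVA.

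**The case against.** The strongest reply is that the planned test is valid and that the gain is unknown and may be trivial. Both parts stand. The interval from baseline to treatment is short ("The time between the pre-intervention measurement and the intervention is less than 15 minutes") and the second record follows within a minute of the intervention, so a high rho is plausible. At 0.9 the gain is about one point of power. Moreover, if the trial is sized from its pilot for the planned test, it meets its power target anyway.

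The power loss and the imbalance shift must also not be added together. The excess variance is 2(1 - rho) - (1 - rho²) = (1 - rho)², which, times 2/n, is exactly the variance of the over-correction term. The shift has random sign and is already inside the change-score standard error.

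Two conditions also hold. Over-correction needs a post-on-baseline slope below 1, which follows from rho < 1 when the SDs are similar. Sections 7 and 8 describe the stance differently, and no stance is stated for the second record, so similar SDs are not assured. And if ANOVA on post values alone were meant, over-correction would not apply, though the baseline would still go unused. The reference to pre-post differences makes that reading unlikely.

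None of this favours keeping the sentence. Rho is unknown and may differ across the 15 outcomes (seven measures with eyes open and closed, plus the Romberg index). In the table ANCOVA gains up to 13 points, and at rho 0.97 it loses about 0.1. Nor does an objective framed as change require a change score: with baseline as covariate, the group effect is the same whether the outcome is the post value or the change.

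**Conclusion.** The concern holds as a matter of efficiency and of conditional balance, not of validity. Under equal SDs, 30 per group and an effect set to give the change score 80% power, ANCOVA adds about 13, 9, 5, 3 and 1 points of power at rho 0.3, 0.5, 0.7, 0.8 and 0.9, and nothing from about 0.97. It also removes the shift from chance imbalance among randomised subjects. The document does not supply rho, so the real gain cannot be stated and may be small. The change should be made because it costs almost nothing. The statements about validity and balance do not cover the 10 pilot subjects, of whom the SAP says "These subjects will be assigned to the same group" and who may enter the final sample. They would be 10 of 30 (33%) or 10 of 35 (29%) of that arm. Neither ANOVA nor ANCOVA is protected by randomisation for them; that is a separate and more serious defect.

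**What to change.** Replace the ANOVA sentence in the SAP with:

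> The between-group effect will be estimated for each variable by ANCOVA of the post-intervention value on group, with the pre-intervention value of the same variable as covariate, and reported as an adjusted mean difference with 95% CI.

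This costs one sentence and one degree of freedom, with no extra data or subjects. It also supplies a between-group estimate and interval, which the SAP does not specify at present. Fixing the model in advance removes any choice between adjusted and unadjusted results after an imbalance has been seen. The sentence does not settle whether pilot subjects are analysed or which of the 15 outcomes is primary; both need their own decision in the SAP.

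### The between-group ANOVA on pre-post differences states no scale and no baseline adjustment; if the positive sway measures behave proportionally this costs power, by an amount the documents do not fix

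*Combined protocol and SAP*

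**What the plan says.** The analysis paragraph of the Statistical Analysis Plan lists assumption checks: "To prove normality, the Kolmogorov-Smirnov test, or Shapiro-Wilk test, and for homoscedasticity the Levene test". For change within a group it then offers two branches, beginning "To evaluate the pre-post intra-group differences, the t test will be used for related samples (if they are parametric", with a rank test as the other branch. For the comparison between groups it says only: "For the analysis of pre-post intergroup differences the ANOVA statistic will be used". It does not mention a transformation, the pre value as covariate or a standard error that allows unequal variances. It also gives no consequence of the checks for this test.

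Protocol section 5.2 lists seven stabilometric variables, each with eyes open and closed, plus the Romberg index. They include path length, "Surface of the ellipse" and three speeds. Section 3 expects this size: "The sample required for this project according to similar articles will be around 30 subjects per group". The SAP leaves the variability to a 10-subject pilot: "This pilot study will provide us with the estimates of the mean and variance of the response variable". Neither part of the document gives an SD, a pre-post correlation or a target difference for any outcome.

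**The concern.** The randomised comparison answers the trial's question, and its analysis is the least specified. Read plainly, it is a test of raw change (post minus pre) between two groups. With two groups and two times, that equals the group-by-time test.

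Most of the outcomes cannot be negative. The area of an ellipse is proportional to the product of its two axes, and the Romberg index is a ratio. Such measures may be right-skewed, with error and effect that grow with the subject's own level. If so, a few subjects with large sway dominate the variance of raw change, and a real proportional effect is harder to detect. An unadjusted change score also gives up precision whenever the pre-post correlation is below 1. With about 30 per group and an 80% power target, either loss could matter. Leaving the scale open also allows it to be chosen for 15 outcomes after the data are seen.

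**Working it through.** **1. The plan's own figure.** The 30 per group cannot be reproduced, because no difference or SD is given. Solved backwards (two-sided 5%, equal groups, both assumed), 80% power needs a standardised difference in change of (1.960 + 0.842) × √(2/30) = 0.723, or 0.736 with the noncentral t.

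**2. Outcomes.** 7 variables × 2 eye conditions + Romberg = 15. Positive by construction: length, ellipse area and three speeds (5 × 2) + Romberg = 11. The X and Y means (2 × 2 = 4) may be signed, and logs are not available for them.

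**3. Assumptions, none from the documents.** Lognormal pre and post values with log SD σ from 0.15 to 0.7; pre-post correlation ρ from 0.5 to 0.9; an effect that multiplies the post value by r. In each case r is set so that log change has 80% power with 30 per arm.

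**4. One case by hand: σ = 0.5, ρ = 0.7.**
- SD of log change = 0.5 × √(2 × 0.3) = 0.387. Log effect = −0.736 × 0.387 = −0.285, so r = 0.752.
- Take raw change in units of the common pre-intervention mean. The difference in means is 1 − r = 0.248.
- Control variance = 2(e^{σ²} − e^{ρσ²}) = 2(1.2840 − 1.1912) = 0.1856.
- Intervention variance = (1 + r²)(e^{σ²} − 1) − 2r(e^{ρσ²} − 1) = 1.5655 × 0.2840 − 1.504 × 0.1912 = 0.1570.
- Noncentrality = 0.248 / √((0.1856 + 0.1570)/30) = 2.32. Power ≈ Φ(2.32 − 2.00) ≈ 63%. Simulation gives 64 to 65%, against 80% for log change.
- For log change the noncentrality is 0.736 × √15 = 2.85. Matching it on the raw scale takes about (2.85/2.32)² = 1.51 times the subjects.

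**5. Full grid.** Simulation, 20,000 trials per cell. Power in %, with ranges over ρ = 0.5 to 0.9; ANCOVA means post on group and pre.

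| Log SD (CV) | Raw change | Log change | Loss | Raw ANCOVA | Log ANCOVA | Gap |
|---|---|---|---|---|---|---|
| 0.15 (0.15) | 78 | 80 | 2–3 | 81–90 | 82–90 | up to 1 |
| 0.3 (0.31) | 72–74 | 80 | 6–8 | 78–88 | 81–89 | 2–3 |
| 0.5 (0.53) | 63–67 | 80 | 14–17 | 73–84 | 81–90 | 5–9 |
| 0.7 (0.80) | 53–56 | 80 | 24–27 | 65–79 | 81–90 | 10–16 |

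Scale and adjustment together put log ANCOVA 3 to 36 points above the planned test on this grid.

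**6. Level.** With no effect, raw change rejects in about 4.5 to 5.2% of trials.

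**7. Other remedies.** Welch's test matches the ANOVA to about 0.3 points. Mann-Whitney on raw change gives 71–74% at σ = 0.3 and 61–65% at 0.7, so it recovers little or only part of the loss.

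**8. The opposite truth: additive effects, normal data, planned test at 80%.** Up to CV 0.2, log ANCOVA is within a point of the planned test or better. At CV 0.3 and ρ = 0.9 it has 73 to 76%. At CV 0.4 and ρ = 0.9 it has about 68%, a loss of 12 to 13 points, when values are floored at 5% of the mean. The loss runs from about 10 to 17 points as the floor moves from 10% to 2%. Raw ANCOVA has 81 to 90% throughout. A normal variable with CV 0.4 falls below zero with probability Φ(−2.5) = 0.6%, so this case strains the model for a positive measure.

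**The case against.** Positive does not mean lognormal, and the documents nowhere say that sway effects are proportional. The argument from the product of two axes applies to the ellipse, not to length or speed. The raw scale keeps the original units, holds its level, works for signed X and Y means, and is the better scale if effects are additive. The SAP is silent on scale and does not commit to untransformed data. Levene's test has no role in a paired comparison, so the checks may well be meant for the ANOVA. All of this stands, and it makes the point conditional.

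A reader might infer three stronger things that the documents do not support.
- *That the plan gives up a definite 12 to 26 points of power for no benefit.* That range needs a log SD of about 0.4 to 0.7, unadjusted change scores and proportional effects. The documents give none of these as inputs, and step 8 shows that the raw scale can have a benefit.
- *That the missing piece is a nonparametric branch between groups.* The within-group branch is a contingency, not evidence that skewed data are expected. Choosing the test from a normality check is not the remedy either, and on that count a single unconditional test is the better practice.
- *That the whole loss is a matter of scale.* The last column of the table shows that much of it disappears once both analyses adjust for baseline.

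The fixed 30 is also a premise. If the pilot's raw variance sets the final size, the cost is extra subjects rather than lower power.

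**Conclusion.** The concern holds in conditional form. As written, the randomised comparison is an unadjusted ANOVA on pre-post differences with no stated scale, for 15 outcomes of which 11 are positive. Its validity is not in question. What it may cost is power, as in the table, and the size depends on a log SD and a correlation that the documents do not give. At a log SD of 0.3 or less the scale matters little once baseline is in the model; at 0.5 or more it matters clearly. Baseline adjustment helps in every case examined, on either scale. The log scale is a reasoned default for the positive outcomes, not a result that follows from the documents. This should be changed, but leaving it does not invalidate the trial.

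**What to change.** Replace the sentence on the between-group analysis with:

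> Each outcome will be compared between groups by a linear model of the post value on group and the pre value. Length, ellipse surface, speeds and the Romberg index will be analysed on the natural-log scale and reported as the ratio of geometric means (intervention/control) with 95% CI; mean X and Y positions stay untransformed. Robust standard errors will be used, and no normality or variance pre-test will select the analysis. The same model on the raw scale will be reported as a sensitivity analysis.

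The cost is SAP wording, one computed variable per log-scale measurement, and a check that the chosen SPSS procedure offers robust standard errors. Two downsides should be stated. Effects on the log scale are read as percentage changes. If effects are in fact additive and normal with a CV of 0.3 to 0.4, the log analysis can lose up to about 13 points against the planned test (step 8 gives the dependence on values near zero). The raw-scale sensitivity analysis covers that case. The pilot's log SD and pre-post correlation should be reported, so that the conditional range can be replaced by a figure.
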